Control variables. We will collect information on social determinants of health that may affect parenting and child behavior outcomes. The social determinants of health are: general demographics, income and economic hardship, and neighborhood and community characteristics.⁶⁹ Demographics (e.g., age, race/ethnicity, household structure) will be collected using a 21-item demographic inventory. Income and economic hardship will be assessed with a 9-item income inventory and an economic hardship scale (7 items).⁷⁰ In our current study, Cronbach's alpha for the economic hardship scale was .68. Neighborhood and community characteristics will be collected using 9 items from the National Survey of Children's Health.⁷¹ Questions include perceived neighborhood social support, condition, and safety.

Outcome variables. Primary parenting outcome variables include parenting behavior, self-efficacy, and stress. The primary child outcomes are child behavior problems and prosocial behavior. All survey data are obtained by parent self-report and will be collected at each of the 4 data collection time points (baseline, 3, 6, and 12 months post baseline). Parenting behavior will include parenting discipline strategies and positive parenting

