behavior. Parenting discipline strategies will be measured using the 40-item Parent Questionnaire (PQ). Three scales – warmth, follow-through on discipline, and corporal punishment – using a 5-point scale measure how parents discipline their children. Cronbach's alpha for the three subscales are .84, .80, and .68, respectively.¹⁴ The PQ is a valid measure of parenting behavior and discipline skills in African American and Latino families.^{14,72} Positive parenting behavior will be assessed using the 21-item Parenting Young Children (PARYC) measure using a 7-point scale. There are three subscales for the PARYC: supporting positive behavior, setting limits, and proactive parenting. Cronbach's alpha for the three scales are .78, .79, and .85, respectively.⁷³ Parenting self-efficacy will be evaluated using the 17-item Parenting Sense of Competence Scale (PSOC). The PSOC has two subscales using 6-point scales: satisfaction (person's liking of the parenting role) and efficacy (person's perceived competence in the parenting role). Cronbach's alpha for the total scale, satisfaction, and efficacy subscales are .79, .80, and .80, respectively.^{74,75} The PSOC is correlated with other measures of family life and child behavior, and the satisfaction subscale is strongly correlated with measures of child behavior, parent well-being, and parenting style.^{74,76} Parenting stress will be assessed with the Parenting Stress Index-Short Form (PSI-SF). The PSI-SF is a 36-item survey with three scales using a 5-point scale: parental distress, parent-child dysfunction, difficult child.⁷⁷ Cronbach's alpha is .90 for the total scale, .79 for parental distress, .80 for parent-child dysfunction, and .78 for difficult child.⁷⁸ The PSI-SF is a valid measure of parenting stress in multicultural samples and for parents from lower socioeconomic groups.^{79,80}

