To determine the effectiveness of the implementation strategy and inform dissemination of the eCPP, a cascaded probability model will be constructed.^{97,98} This will be developed based on the following proportions: (a) the likelihood of clinician adoption at the site [*proportion 1 (pr 1)*], (b) the likelihood of implementation (study introduction) by clinicians at the site [*pr 2*], (c) the likelihood of parent enrollment in the study [*pr 3*], and (d) the likelihood of maintenance of behavior change by the eCPP participants [*pr 4*]. *Pr 4* is defined as the proportion of participants whose parenting and child behavior outcomes are the same or improved at the 12-month data collection compared to the 6-month data collection. The estimated likelihood of parents being introduced to the program will be the product of *pr1* and *pr2*. Second, the compound likelihood of parent enrollment in the study will be the product of *pr1*, *pr2*, and *pr3*. Finally, we will estimate the compound likelihood of maintaining behavior change by examining the product of *pr1*, *pr2*, *pr3*, and *pr4*. This analysis will provide us with two important pieces of information: (1) the probable benefits of the program in terms of how likely it is for parents to achieve maintenance of behavior change and (2) inform us of the phase of the implementation process (as operationalized by *pr1*, *pr2*, *pr3*, and *pr4*) which is likely to interfere with the dissemination of the eCPP.

We will conduct a content analysis of the post-implementation interviews with the clinicians. We will use a coding-based system of content obtained from the interviews using the notes taken during the interview using Atlas.ti software. Atlas.ti allows for the identification, organization, and systematizing of codes that can then be assessed in the context of the clinician interviews. Themes will be summarized by site and used to inform the development of processes and procedures to support the implementation and dissemination of the eCPP in pediatric primary care practice sites.

Bibliography & References Cited

1. Children's Defense Fund. Child poverty in America 2013: State analysis. <http://www.childrensdefense.org/zzz-child-research-data-publications/data/child-poverty-in-america-1.pdf>. Updated 2014. Accessed January 12, 2015.

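### The pr4 maintenance rule has no margin for measurement error, so the cascade understates maintenance even when every parent truly holds steady

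*Combined protocol and SAP*

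**What the plan says.** The Aim 3 section of the analytic plan builds a cascade from four proportions: clinician adoption (pr1), study introduction (pr2), parent enrollment (pr3) and maintenance among eCPP participants (pr4). The section takes pr4 to be "the proportion of participants whose parenting and child behavior outcomes are the same or improved at the 12-month data collection compared to the 6-month data". It does not define what counts as the same, gives no tolerance, and does not say which scales are used or how they are combined.

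The plan then states that "we will estimate the compound likelihood of maintaining behavior change by examining the product of" all four proportions. Besides the likelihood of maintained change, the model is meant to "inform us of the phase of the implementation process", meaning the phase "which is likely to interfere with the dissemination of the eCPP".

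The outcomes are set out under Measures, Outcome variables: "Primary parenting outcome variables include parenting behavior, self-efficacy, and stress", and "The primary child outcomes are child behavior problems and prosocial behavior". That makes five primary constructs, all measured by multi-item parent questionnaires. The same section reports their reliability. For the Parent Questionnaire, for example, "Cronbach's alpha for the three subscales are .84, .80, and .68, respectively".

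**The concern.** Questionnaire scores vary from visit to visit without any real change. A cut-off at exactly zero change turns that variation into a classification: a stable parent whose 12-month score is one point worse than the 6-month score counts as not maintaining. If several scores must all be no worse, the chance of passing falls further with each score added, although nothing about the parent has changed.

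What is at stake is the use made of the cascade. Its product is to be read as the probability of lasting benefit, and its smallest factor as the obstacle to dissemination. A factor that falls well short of 1.0 under perfect maintenance distorts both readings.

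**Working it through.** The documents give no expected value for pr4, so there is no figure to reproduce. The check asks what pr4 would be if no parent truly changed between 6 and 12 months, when a correct rule would return 1.0.

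**Inputs from the documents.** Five primary constructs; 156 eCPP parents (Study Design); item counts, response ranges and alphas (Measures).

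**Assumptions not in the documents.** Symmetric error; correlation ρ of the changes across scores from 0 to 0.8; tie rates as shown; for the simulation, a score SD of 10-20% of the scale range and a reliability of .80 for a PARYC total.

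**Step 1: one score.** With symmetric error and no true change, P(same or improved) = (1 + P(tie))/2.
- No ties: 0.50. With 10% ties: 1.10/2 = 0.55.
- Simulated integer scores give about 0.52-0.54 on the long scales (PARYC, PSOC, PSI-SF, ECBI Intensity).
- Coarser scores tie more often: 0.63-0.74 for SDQ prosocial and 0.68-0.80 for the ECBI Problem Scale.

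**Step 2: several scores jointly, no ties.** For two scores the probability is 1/4 + arcsin(ρ)/(2π). For k scores it is 0.5^k at ρ = 0 and 1/(k+1) at ρ = 0.5; other values come from numerical integration. For k = 5, 0.5^5 = 0.031 and 1/6 = 0.167. The last two columns multiply by 156.

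| ρ (assumed) | Two scores | Five constructs | Of 156, two scores | Of 156, five |
|---|---|---|---|---|
| 0 | 0.250 | 0.031 | 39 | 5 |
| 0.3 | 0.298 | 0.105 | 46 | 16 |
| 0.5 | 0.333 | 0.167 | 52 | 26 |
| 0.8 | 0.398 | 0.291 | 62 | 45 |

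**Step 3: sensitivity (ρ from 0 to 0.8 unless stated).**
- With 10% ties: 0.30-0.45 for two scores and 0.05-0.34 for five.
- Simulated integer scores: 0.26-0.42 for PARYC plus ECBI Intensity, and 0.04-0.34 for one score per construct. The most lenient pair tried, PARYC plus ECBI Problem, gives 0.35-0.50.
- Two scores reach 0.50 only with ties of about 20% (ρ = 0.8) to 42% (ρ = 0).
- If every score truly went on improving by 0.5 SD of the change score, two scores would still give only 0.48-0.55 and five 0.16-0.36 (ρ from 0 to 0.5).

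**Step 4: effect on the product.** The cascade is pr1 × pr2 × pr3 × pr4, so any shortfall in pr4 passes through in proportion. At pr4 = 0.50 the compound likelihood is halved; at 0.167 it is one sixth of what it should be.

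**Step 5: a rule with a tolerance.** Count worsening only beyond 1.645 × SD × √(2(1 − reliability)). At reliability .80 the SD of the change error is √0.4 = 0.632 SD, and the limit is 1.645 × 0.632 = 1.04 SD. A stable parent is then classed as maintaining 95% of the time on one score. A parent with a true 0.5 SD decline is still classed as maintaining with probability Φ((1.04 − 0.50)/0.632) = Φ(0.85), about 0.80.

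**The case against.** The strongest reply is that the joint condition is inferred. The definition contains no word such as all and no combining rule. Elsewhere the plan uses parenting and child outcomes as a collective label for work done one outcome at a time: the growth models take the outcome being tested, and the cost-effectiveness section speaks of ratios in the plural. This stands in part. One pr4 in one product favors the joint reading, but a separate pr4 per outcome is not excluded. On that reading it would be wrong to say that most stable parents fail; about half or more would pass. A pr4 of 0.50-0.55 where 1.0 is correct is still a large bias.

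Three stronger readings are tempting, and the documents do not support them:

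- *All 18 subscales must hold* (3 + 3 + 2 + 3 + 2 + 5 across the instruments). At ρ = 0.5 this would give 1/19 = 0.053, and at ρ = 0 almost nothing. Nothing says that pr4 uses every subscale, and the plan reports total-scale alphas for PSOC and PSI-SF.
- *Low reliability drives the result.* Without ties, a stable parent's chance of scoring worse is one half at any reliability. Reliability enters only through ties and through the width of a tolerance.
- *pr4 is bound to be the weak phase.* The documents give no values for pr1 to pr3, any of which could be lower.

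It is also fair that Aim 3 is descriptive and that maintenance is formally tested by the planned contrasts for Hypothesis 1B. That limits the consequence, but those contrasts do not feed pr4 and so do not correct the cascade.

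**Conclusion.** The concern holds in a bounded form. Applied as written, the rule gives truly stable parents an expected pr4 well below 1.0 whether it is used on one score or jointly on several. The single-score result needs only symmetric error and the tie rate. The joint figures also rest on the assumed correlations and on a reading that the text suggests but does not state.

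The downward bias is established for parents who hold steady. Parents who truly decline can be misclassified in the other direction, so the net error in a mixed group is not determined here. Under perfect maintenance, pr4 and the compound likelihood are too low, and maintenance can be wrongly named as the limiting phase, depending on pr1 to pr3. No Aim 1 estimate or test is affected. The definition should be changed, but the trial's main inference does not depend on it.

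**What to change.** Before 12-month data are examined, reword the pr4 definition:

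1. Name one score for each primary outcome. For parenting behavior this means choosing among six subscales on two instruments, or defining a total.
2. Compute pr4 and the cascade separately for each named score.
3. Beside each pr4, print the value expected when no parent truly changes (for one score, half of one plus the tie rate) and the mean 6-to-12-month change.
4. As a sensitivity analysis, report pr4 counting worsening only beyond a prespecified reliable-change limit, for example 1.645 × SD × √(2(1 − reliability)). Preferably estimate the error of change from the trial's own repeated control-arm data: Cronbach's alpha measures internal consistency, and error over six months is probably larger than it implies.

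No new data are needed. The cost is several cascades instead of one. The tolerance version also misses moderate declines: at reliability .80, about 80% of parents with a true 0.5 SD decline would still count as maintaining. It should therefore accompany the mean change, not replace it.

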Study Design. The study will be a person-randomized clinical trial comparing the effects of the eCPP tablet-based intervention to an enhanced usual care control condition (Table 1). Parents ($n = 312$) of 2- to 5-year-old children will be recruited from 4 primary care practices and randomly assigned to either the eCPP or control condition. Randomization will occur within sites at the participant level. Intervention parents ($n = 156$) will complete the 6 modules of the eCPP over a period of 3 months (~2 weeks/module; intervention phase) with ongoing access to the program (reference phase) throughout the remainder of the study period. Control condition parents ($n = 156$) will receive tablet-based parenting materials that they would normally receive at their primary care practice (e.g., information regarding nutrition, immunization, and exercise) and have access to the materials over the same intervention time period. Data collection in both conditions will occur at baseline and at 3, 6, and 12 months post-baseline. A descriptive design will be used to evaluate implementation of the eCPP from the perspective of practice sites, clinicians, and parents. Guided by the RE-AIM framework, we will use surveys, electronic health records, data usage metrics, and post-implementation assessments to evaluate the implementation process over the study period.

Measures.

Aim 1: Randomized Control Trial. All measures are written at the 5th grade reading level and administered on an Android tablet as computer assisted, self-interviews (CASIs). An audio option (audio-CASI) is available if parents prefer to listen to the questions. All control and outcome data are obtained by parent self-report and will be collected at each of the 4 data collection time points (baseline, 3, 6, and 12 months post baseline). Previous findings from RCTs of the group-based CPP have found significant findings across three sources of data: parent self-report, teacher report and parent-child observation.^{14,24} In these studies, the parent self-report findings have consistently agreed with other methods of measuring parent and child outcomes. For this reason, the source of parenting and child outcome data for this study will be parent self-report alone.

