We will measure child behavior problems using the Eyberg Child Behavior Inventory (ECBI).⁸¹ The ECBI is a 36-item scale designed to measure the presence and intensity of problem behavior. Each item is measured on two scales: the Problem Scale (dichotomous) and Intensity Scale (7-point). The ECBI is a valid measure of child behavior problems, with established convergent validity across racial and ethnic populations and economically and linguistically diverse samples.⁸¹⁻⁸³ Cronbach's alpha reliabilities of the Intensity and Problem Scale scores are .92 and .99.²⁴ In addition, the Strengths and Difficulties Questionnaire (SDQ) will provide a measure of child behavior problems and prosocial behavior. The 25-item SDQ has a five-factor structure (emotional, conduct, hyperactivity-inattention, peer, and prosocial) using a 3-point scale. Mean Cronbach's alpha for the SDQ is .73.⁸⁴ The SDQ has been validated in multiple cultures and socioeconomic levels.⁸⁵

Aim 2: Cost effectiveness analysis. Data for the cost effectiveness analyses will be drawn from invoices, staff report, study records, EHR, and eCPP electronic time stamps (Table 4). Resources used for the

Table 4. Description of Resource and Cost Measures

Cost Category	Source	Unit of Measure	Translation to Costs
eCPP costs			
eCPP delivery costs	Invoice	Participant	Average cost/participant
Orientation delivery costs			
EHR modification	Programmer report	Minutes/site	Programmer average hourly wage
Clinician time receiving study orientation	Study records	# of clinicians Minutes/clinician	Clinician average hourly wage
Time to lead orientation	Study records	Minutes	Study staff average hourly wage
Clinician costs			
Time to introduce study*	EHR	Minutes/ participant	Clinician average hourly wage
Parent costs			
Time spent learning about the study*	EHR	Minutes/ participant	Parent average hourly wage
Time spent completing eCPP modules	digital time logs	Minutes/ participant	Participant average hourly wage

EHR = Electronic Health Record; *time for introducing and learning about the study includes all parents (non-participants and participants), averaged across the # of participants.

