All analyses for Aim 1 will be performed on an intent-to-treat basis. As multiple dependent variables are being examined, a repeated-measures multivariate analysis of variance (assessment x intervention condition) will be conducted to ensure control of experiment-wise Type-I error, and to perform an initial assessment of intervention effects. We will then test intervention efficacy using multilevel growth models⁹⁰⁻⁹² with three levels (assessments [Level 1] within parent [Level 2] within primary care practice site [Level 3]). Intervention condition will be dummy coded (eCPP vs. control) at Level 2, and covariates at site-level (e.g., clinic size) or parent-level (e.g., age, race/ethnicity) will be included at the appropriate level of analysis. By including baseline measures of the outcome variable being tested as a covariate at Level 2 (parent level) and setting the intercept at the 3-month assessment, we will be able to test Hypothesis 1A (intervention effects between baseline and 3-month assessment) as the main effect of intervention condition (i.e., controlling for baseline level of the outcome being tested). The condition x time interaction will then serve to test differential change in outcome measures following the 3 months of active intervention, and planned contrasts will be estimated to test Hypothesis 1B (maintenance of intervention effects at 6 and 12 months).

Aim 2. Compare the cost-effectiveness of the eCPP intervention relative to control for parenting and child outcomes. **HYPOTHESIS 2:** The eCPP is cost-effective relative to control for parenting and child outcomes.

We will assess cost-effectiveness of eCPP from the societal perspective, including costs borne by the program, health care system, and parent. We will conduct additional analyses from the program, health care system, and parent perspectives separately. For the cost measurement, quantities of resources used and their associated prices will be collected for the eCPP (either prices paid or value of the clinician time) and participant (i.e., value of participant's time to use the eCPP). Program and parent costs will be calculated for the 12-month study duration and summed to calculate total cost per parent. All costs will be valued in 2015 dollars.

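### The maintenance proportion (pr4) in the Aim 3 cascade compares 12 months only with 6 months in eCPP parents, so it barely separates a lasting benefit from no benefit

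*Combined protocol and SAP*

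**What the plan says.** In the Analytic plan, Aim 3, four proportions are multiplied in sequence. The first two are clinician adoption at the site and introduction of the study by clinicians. The third, pr3, is "the likelihood of parent enrollment in the study". The fourth, pr4, is labelled "the likelihood of maintenance of behavior change by the eCPP participants" and is the proportion of participants whose parenting and child outcomes "are the same or improved at the 12-month data collection compared to the 6-month data collection".

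The plan takes two things from the cascade. One is "the probable benefits of the program in terms of how likely it is for parents to achieve maintenance of behavior change". The other is the phase of implementation most likely to hold back dissemination.

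Three other places bear on the point.

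- Study Design: "Data collection in both conditions will occur at baseline and at 3, 6, and 12 months post-baseline". eCPP parents complete the modules over 3 months, "with ongoing access to the program (reference phase) throughout the remainder of the study period".
- Analytic plan, Aim 1: Hypothesis 1B (maintenance at 6 and 12 months) is tested by planned contrasts between the arms, adjusted for baseline.
- Table 5, Maintenance row: participant-level maintenance is assigned to that randomized comparison. The contrasts do not enter the four-factor product.

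**The concern.** To maintain a change, a parent must first have changed. Neither pr4 nor the three factors before it asks whether a parent improved from baseline. A parent who never changed, or who got worse by 6 months and stayed there, counts as a success if the 12-month score is no worse than the 6-month score. A parent who gained a great deal by 6 months and kept most of it counts as a failure.

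The product could therefore look favorable for a program with no effect, or unfavorable for one with a real but partly fading effect. It could also point to the wrong phase as the obstacle to dissemination. What is at stake is this descriptive product and how it is read. No Aim 1 or Aim 2 estimate, error rate or sample size depends on it.

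**Working it through.** The plan states no expected pr4, effect size or SD, so there is no figure to reproduce. From the documents come the definition of pr4, the visit schedule and the arm size of 156. Everything else is assumed: one scale scored so that higher is better, total SD 1, a stable true score plus independent error at each visit, an effect of 0.5 SD, and reliability (rel) 0.8 with a range of 0.7 to 0.9. Error variance and availability of visits are taken to be the same in every scenario.

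**Step 1: pr4 as written, continuous score.** Let Y_t = T + d_t + e_t, where d_t is the effect at visit t. Then Y12 − Y6 = (d12 − d6) + (e12 − e6), which has SD s = √(2(1 − rel)), and

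pr4 = Φ((d12 − d6)/s).

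The true score T cancels, and so does any effect that is equal at the two visits. At rel 0.8, s = √0.4 = 0.632.

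| Scenario | d6, d12 (SD) | pr4, rel 0.8 | pr4, rel 0.7 to 0.9 |
|---|---|---|---|
| No effect | 0, 0 | 0.50 | 0.50 |
| Gain kept | 0.5, 0.5 | 0.50 | 0.50 |
| Stable harm | −0.5, −0.5 | 0.50 | 0.50 |
| Gain lost before 6 months | 0, 0 | 0.50 | 0.50 |
| Half the gain lost after 6 months | 0.5, 0.25 | Φ(−0.25/0.632) = 0.346 | 0.373 to 0.288 |
| All the gain lost after 6 months | 0.5, 0 | Φ(−0.5/0.632) = 0.215 | 0.259 to 0.132 |

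Simulations with scores rounded to 0.1 or 0.5 SD, and with two or five outcomes all required to qualify, change the level of pr4. The no-effect, kept-gain and stable-harm cases remain equal within simulation error.

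**Step 2: scores near a limit.** The outcome scales are bounded; the SDQ items, for example, have 3 points. I simulated a score rounded and clipped to 0–10 with SD 2 and a 0.5 SD effect.

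| Reliability | Mean | Harm | None | Kept | Kept − none |
|---|---|---|---|---|---|
| 0.8 | 5 | 0.655 | 0.652 | 0.655 | 0.003 |
| 0.8 | 8 | 0.666 | 0.693 | 0.742 | 0.049 |
| 0.8 | 8.5 | 0.677 | 0.715 | 0.774 | 0.059 |
| 0.7 | 8 | 0.639 | 0.665 | 0.715 | 0.050 |
| 0.7 | 8.5 | 0.649 | 0.687 | 0.749 | 0.062 |
| 0.9 | 8 | 0.720 | 0.744 | 0.788 | 0.044 |
| 0.9 | 8.5 | 0.730 | 0.764 | 0.815 | 0.051 |

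For scale, the 95% half-width of one proportion with 156 parents, 1.96√(p(1 − p)/156), is 0.069 at p = 0.742 and 0.061 at p = 0.815. At mean 8, half the gain lost gives 0.606 (0.596 to 0.618 over the reliability range), still below no effect.

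**Step 3: a proportion tied to baseline.** Let pr4 be the proportion better than baseline at 12 months by at least 0.5 SD, so that pr4 = Φ((d12 − 0.5)/s). At rel 0.8, with no change in controls:

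| Scenario | eCPP | eCPP − control |
|---|---|---|
| Gain kept, or gained late | Φ(0) = 0.500 | +0.285 |
| Half the gain lost | Φ(−0.395) = 0.346 | +0.131 |
| None, or all lost | Φ(−0.791) = 0.215 | 0 |
| Stable harm | Φ(−1.581) = 0.057 | −0.158 |

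The SE of the kept-gain difference is √((0.25 + 0.215 × 0.785)/156) = 0.052, giving a 95% CI of 0.18 to 0.39. With 125 per arm (20% missing, assumed) the SE is 0.058 and the CI 0.17 to 0.40. Near the ceiling (mean 8, 1-point threshold) the order holds: 0.543 kept, 0.428 half lost, 0.307 none, 0.113 harm.

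**The case against.** The strongest reply is that maintenance is a separate RE-AIM component from efficacy. A maintenance measure should fall when scores decline after 6 months, and Table 5 already sends participant-level maintenance to the controlled Hypothesis 1B contrasts. Research Question 3 therefore gets a sound answer whatever pr4 shows. This stands as far as it goes, and it limits the concern to the product. It does not rescue the product, because those contrasts are not one of its factors and the plan still reads the product as program benefit.

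The size also depends on assumed cases. At means of 9 or 9.5 on the same bounded scale (reliability 0.8), kept minus none is about 0.07, above the half-width of about 0.06. At means 8 and 8.5, kept minus harm (about 0.08 and 0.10) also exceeds the half-width. So strong ceiling effects do give some separation, but only by accident of where scores sit.

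The figures use one scale, whereas the plan speaks of several outcomes and gives no rule for combining them. That is a further gap. It moves the level (from about 0.50 with one continuous outcome to 0.03 if five must all qualify) but not the equality across scenarios.

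Finally, the proposed measure has limits of its own. It drops the 6-month visit and needs a threshold: at 0.3 or 0.8 SD the kept-gain difference is 0.31 or 0.22. The eCPP proportion also remains open to trends common to both arms.

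**Conclusion.** The concern holds. With equal shifts at both visits and scores away from the limits, pr4 has the same expectation for no benefit, kept benefit and stable harm. That follows from algebra and does not depend on the assumed effect or reliability; the value 0.50 is for one continuous scale. Near a ceiling, kept exceeds none by 0.04 to 0.06 at means 8 to 8.5, within the sampling error of one proportion in 156 parents. A half-kept benefit scores below no effect in both settings (0.35 against 0.50; 0.61 against 0.69 at mean 8). These sizes rest on assumed inputs throughout, since the documents give no means, SDs or reliabilities for change.

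This should be fixed before the Aim 3 product is reported as evidence of benefit. It does not touch the randomized comparison.

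**What to change.** For each scale separately, or for one scale named in advance:

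- define pr4 as the proportion of all eCPP parents who are better than baseline at 12 months by a preset amount;
- enter that proportion in pr1 × pr2 × pr3 × pr4 and label the product as uncontrolled;
- report the same proportion in the control arm;
- base any statement of program benefit on the eCPP-minus-control difference, outside the product and beside the Hypothesis 1B contrasts.

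The cost is wording. Both arms are already measured at baseline and 12 months, so no new data are needed. A threshold and a rule for missing 12-month scores must be set in advance, and the compound likelihood may come out lower.

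Two limits should be stated in the plan. First, the new pr4 shows net improvement at 12 months and not the path. A late gain, possible because access continues after month 3, scores the same as a kept gain, so the 1B contrasts are needed beside it. Second, the eCPP proportion alone rises with any trend common to both arms. With no effect and an assumed 0.3 SD trend it goes from 0.21 to Φ((0.3 − 0.5)/0.632) = 0.38, which is why the product needs the uncontrolled label and the control-arm proportion is reported.
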